8.2 Expected duration of participation in the trial – Time Frame

CIS patients will be invited to join the trial for 12 months. After agreeing to join the trial, participants will be randomized into two groups. Participants in one group will receive narrow band UVB phototherapy which will be administered 3 times per week for 8 weeks. They will also wear a UVB dosimeter. Participants in the other group will not receive phototherapy but will wear a UVB dosimeter for 8 weeks. Blood will be taken from all participants for biomarker analysis at baseline (before phototherapy commences), and 1 week, and 1, 2 (ie when phototherapy ceases), 3, 6 and 12 months after initiation of phototherapy (see Appendix 1).

One group of the healthy controls will also join the trial for 12 months (those donating blood monthly). In the other group donating blood once for blood cell characterization, they will be

invited for a single blood donation.

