8.3 Accountability Procedures for UVB phototherapy

Prior to commencing narrow band UVB phototherapy, a risk factor profile including previous phototherapy or PUVA treatment, sun exposure history, occupation, personal and family history of skin cancer, and medication will be ascertained. Upon examination, sun damage and presence of skin disease including skin cancers will be documented. Phototherapy will be given three times/week for eight weeks (24 exposures in total). Phototherapy will be delivered according to the Dundee protocol which is based on the patient's skin type. The starting dose of 20 mJ/cm² is chosen based on knowledge of the skin type and will be well below the likely erythema threshold. All patients will start with 40% increments on their initial dose, which will be reduced to 20% increments after 6 exposures. At each visit the dose given and any adverse effects will be recorded.

If a participant develops a confirmed second demyelinating event (confirmed relapse), the participant should be managed by Professors [name] and [name], or other neurologists associated with the study. Subjects will be withdrawn from UVB phototherapy if they experience a significant or serious adverse event, which, in the opinion of [name] or Professors [name] or [name] or other neurologists associated with the study, is related to UVB phototherapy.

The schedule is to give narrow band UVB phototherapy 3 times a week for 8 weeks Participants will be asked to exit the trial if there is more than one week between phototherapy sessions and they cannot complete 24 phototherapy sessions within 12 weeks. We will ask participants to return to the clinic for an early withdrawal/Exit visit.

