8.4 Randomisation

Selection of active treatment versus control subjects will be randomised 1:1 by an independent investigator at the patient Baseline visit, with matching on demographic variables (age and sex) to optimize balance between groups. It will be obvious to the patients into which group they have been randomised.

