10.3 Treatment schedule

Narrow band UVB phototherapy will be given three times/week for eight weeks (24 exposures in total). Narrow band UVB phototherapy will be delivered according to the Dundee protocol which is based on the participant's skin type. The starting dose of 20 mJ/cm² is chosen based on knowledge of the skin type and will be well below the likely erythema threshold. All participants will start with 40% increments on their initial dose, which will be reduced to 20% increments after 6 exposures. At each visit the dose given and any adverse effects will be recorded by [name], or her experienced study nurses.

[name] will assess the skin of the participants before and 6 months after initiation of phototherapy, and during the trial if the participants have any concerns.

Narrow band UVB phototherapy will be initiated as soon as possible for those who are not prescribed a short course (few days) of glucocorticoids for treatment of their first demyelinating event.

If participants randomised to receive narrow band UVB phototherapy have been given a short course of glucocorticoids to treat their symptoms, the participants will be asked to commence UVB phototherapy in one month after completion of glucocorticoids. This will allow a drug-washout period and normalization of their immunological biomarkers. After this 'washout period' and immediately prior to the start of phototherapy, they will be asked to donate 50 ml blood for pretherapy measurement of biomarkers and collection of peripheral blood mononuclear cells for functional assays.

All participants will be required to wear a UVB dosimeter for 8 weeks. The UVB dosimeters will be used to collect daily UVB exposure data for these participants.

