19.1 Intention to treat-definition

Participants who have undergone 2 weeks (6 sessions) of narrow band UVB phototherapy will qualify for intention-to-treat analysis.

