19.3 Sample size

Our power calculations assume recruitment of 30 subjects to receive UVB phototherapy and 30 patients to not receive phototherapy (but allow study of seasonal effects). If new MRI lesions are expected in 90% of CIS patients over 1.5-2 years (CHAMPS, ETOMS, BENEFIT, PRECISE studies), then a treatment effect (ie reduction of 10%) should be discernible with a sample size of 30 patients. Power calculations for analysis of a biomarker (transcriptome) change based on standard deviation and means for each gene in winter indicated that between 11 and 27 patients need to be compared for a P<0.05.

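### The set labelled intention-to-treat is defined by receiving 6 UVB sessions: read literally it admits no controls, and read charitably it excludes randomised patients from the UVB arm only

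*Protocol*

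**What the plan says.** Section 19.1, headed as the definition of intention to treat, consists of one sentence: "Participants who have undergone 2 weeks (6 sessions) of narrow band UVB phototherapy will qualify for intention-to-treat analysis". The Statistical Analyses entry of the synopsis (section 4) repeats it word for word, so it is not a slip in one place. No other section defines an analysis set, and none admits all randomised participants.

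The sections that bear on it are these:
- **Allocation.** Section 8.4: patients "will be randomised 1:1 by an independent investigator at the patient Baseline visit". Section 8.8 places randomisation at the screening visit instead. Both precede the first session.
- **UVB arm.** Section 8.3: "Phototherapy will be given three times/week for eight weeks (24 exposures in total"). For those given steroids for the first event, section 10.3 says "the participants will be asked to commence UVB phototherapy in one month after completion of glucocorticoids".
- **Control arm.** Section 8.2: "Participants in the other group will not receive phototherapy but will wear a UVB dosimeter for 8 weeks".
- **Planned numbers.** Section 19.3: "Our power calculations assume recruitment of 30 subjects to receive UVB phototherapy and 30 patients to not receive phototherapy".
- **Planned test.** Section 19.4.1 compares the groups by assignment, with a proportional hazards model and a log-rank test. It names no analysis set.

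**The concern.** An intention-to-treat set is fixed at randomisation. Here, entry depends on attendance and exposure after randomisation, and only one arm can meet the condition. The protocol gives ways to fall short that exist only in the UVB arm. Phototherapy stops for adverse events judged related to it (sections 8.3 and 15), and patients who miss too many sessions are asked to exit (sections 8.3 and 15.1). Patients also know their arm (section 8.4), so refusal can depend on allocation.

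If those who stop before session 6 differ in prognosis from those who continue, the UVB group that is analysed is a selected one while the control group is not. The difference between arms then mixes treatment with selection. A report calling this analysis intention-to-treat would tell readers that the randomised comparison was preserved when it was not.

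**Working it through.** **Step 1. The rule applied to each arm.** Three sessions a week for 2 weeks is 3 x 2 = 6, and for 8 weeks 3 x 8 = 24, so the rule agrees with the schedule. Let k be the number of UVB patients with fewer than 6 sessions.

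| Reading | UVB analysed | Control analysed |
|---|---|---|
| Literal | 30 - k | 0 |
| Charitable (controls kept) | 30 - k | 30 |
| All randomised | 30 | 30 |

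The protocol gives no value for k. Patients who stop after session 6 still meet the rule, so the exclusion concerns only stopping before session 6. The steroid washout does not itself exclude anyone, but it can lengthen the interval between allocation and session 6.

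**Step 2. A 12-month risk.** Section 19.3: "If new MRI lesions are expected in 90% of CIS patients over 1.5-2 years". Assuming a constant hazard, and using the lesion figure as a stand-in for the composite event, the 12-month risk is 1 - 0.1^(1/T), with T in years:
- T = 1.5: 1 - 0.1^(1/1.5) = 0.785
- T = 2: 1 - 0.1^(1/2) = 0.684

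The range is therefore about 68-78%.

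**Step 3. Spurious difference under the charitable reading, with no UVB effect.** Let p be the risk in both arms as randomised and r the risk among the k excluded. The risk among the UVB patients left is (30p - kr)/(30 - k), and the spurious benefit is p minus that.

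Example, p = 0.68, k = 3, r = 1.0: (20.4 - 3)/27 = 0.644, so the shift is 0.036.

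| k | r | p = 0.68 | p = 0.78 |
|---|---|---|---|
| 3 | equal to p | 0 | 0 |
| 3 | 0.90 | 0.024 | 0.013 |
| 3 | 1.00 | 0.036 | 0.024 |
| 6 | equal to p | 0 | 0 |
| 6 | 0.90 | 0.055 | 0.030 |
| 6 | 1.00 | 0.080 | 0.055 |

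This gives about 1-4 points for 3 stoppers and 3-8 points for 6 stoppers when the stoppers are high-risk. The direction is not fixed. At p = 0.70 with 3 stoppers who would have had no event, the UVB rate becomes 21/27 = 0.778, a shift of 7.8 points against UVB.

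**Step 4. Chance of a significant result favouring UVB when there is no effect.** Exact binomial enumeration, pooled z-test, two-sided 5% (assumed, since section 19.3 gives no alpha for this endpoint), p = 0.70, 30 controls and 30 - k UVB patients:

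| Excluded UVB patients | Chance |
|---|---|
| None | 2.4% |
| 3, average risk | 3.0% |
| 3, all would have events | 5.3% |
| 6, all would have events | 9.5% |

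The values of k and r are illustrations, not figures from the protocol. The z-test stands in for the planned log-rank and proportional hazards analyses.

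**The case against.** The best defence is that the authors plainly meant 30 against 30 and intended the rule for the UVB arm only, as an exposure threshold. The first part is fair: nobody planned an analysis without controls. It does not rescue the definition, because on that reading exclusion still falls on one arm, after randomisation. Nor is this something left to a statistical analysis plan, since the protocol itself fixes the rule.

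The defence on size is stronger and largely stands. Nothing in the protocol ties missing 6 sessions to MRI or relapse risk. Under the constant hazard of step 2, the yearly hazard is ln(10)/T = 1.15 to 1.54, so the chance of an event in any two weeks is 1 - exp(-hazard x 2/52), about 4-6%. Events in that window could not by themselves make 10-20% of patients stop. With stoppers of average risk the bias is zero.

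A reader might infer more than the text supports:
- **That the safety summary loses early stoppers.** Section 19.1 concerns the intention-to-treat analysis. Sections 10.5 and 18.4 record adverse events from consent, and section 19.2 has the board review all serious events, all reported events in summary and all withdrawals.
- **That the cut-off falls where intolerance peaks.** No section gives the timing of intolerance. Section 10.3 describes the starting dose as well under the expected erythema threshold, with increments after that.
- **That relapse ends phototherapy early.** Sections 8.3 and 15.1 refer relapsing patients to the neurologists for management and do not make relapse a stopping rule.
- **That all five primary endpoints use this set.** Section 19.4 names no set. It is the only one defined, but its reach is an inference.

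**Conclusion.** The definition is wrong as written and should be corrected before analysis. This follows from the text and does not depend on the illustrations: the set either contains no controls or is selected in one arm by post-randomisation exposure.

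How much bias results is unknown. Under the assumptions shown, it runs from none to about 8 percentage points in favour of UVB, and it could run the other way if stoppers have a better prognosis. For scale, the trial seeks a 10% reduction, which section 19.3 does not identify as absolute or relative. It would go too far to say that the randomised comparison is necessarily destroyed: if few patients stop before session 6, or stop for reasons unrelated to outcome, the practical effect may be small. What is lost is the protection that randomisation gives, and with it the right to the label.

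**What to change.** Replace the sentence in section 19.1 and in the synopsis with: *The intention-to-treat set is all randomised participants, analysed in the arm assigned, regardless of the number of sessions received.* Keep the set with 6 or more sessions only as a labelled sensitivity analysis, and state how controls enter it.

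The wording costs two sentences, and the estimate may be less favourable to UVB. No patients are added. The definition alone is not enough, however. UVB patients who cannot complete 24 sessions in 12 weeks are asked to exit and then have one early termination visit (sections 8.3, 10.4.5 and 15.1), so their 12-month outcomes would not exist. Either the outcome visits already in the schedule should continue for those who agree, with stopping phototherapy kept distinct from leaving follow-up, or the plan should state how missing 12-month outcomes are handled. Neither option changes when phototherapy is given or stopped.

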19.2 Safety monitoring and analysis

The independent Data Safety Monitoring Board will review all serious adverse events individually and unblinded, all reported adverse events in summary format and all study withdrawals. The Data Safety Monitoring Board may recommend cessation of the study due to safety concerns at any time. It is envisaged that the Data Safety Monitoring Board will meet 6-monthly by teleconference (or as required), to be convened by the Co-ordinating Principal Investigator. The Data Safety Monitoring Board will consist of an independent neurologist ([name]), a dermatologist and an endocrinologist.

19.3 Sample size

Our power calculations assume recruitment of 30 subjects to receive UVB phototherapy and 30 patients to not receive phototherapy (but allow study of seasonal effects). If new MRI lesions are expected in 90% of CIS patients over 1.5-2 years (CHAMPS, ETOMS, BENEFIT, PRECISE studies), then a treatment effect (ie reduction of 10%) should be discernible with a sample size of 30 patients. Power calculations for analysis of a biomarker (transcriptome) change based on standard deviation and means for each gene in winter indicated that between 11 and 27 patients need to be compared for a P<0.05.

19.4 Analysis Plan

19.4.1 Time to Event Analysis

For all time-to-event analyses (time to recurrent demyelinating event, recurrent clinical relapse,

three- month confirmed disease progression, 12 month recurrent disease activity rates), we will determine the hazard ratio of their development at 12 months, adjusted for known important covariates, namely age, sex, multifocal/unifocal onset, T2 lesion number at baseline (<9, 9+), Gadolinium-enhanced lesion number at baseline (0,1,2+), and use of intravenous methylprednisolone to treat first demyelinating event. This analysis will utilise a proportional hazard regression model. Additionally, Kaplan-Maier plots will be constructed and difference between treatment assignations tested by log-rank test for trend. Analyses will also be adjusted for variables we are collecting in the study questionnaires (eg. estimated dietary calcium and vitamin D intake, recent sun exposure, remote sun exposure, skin type), and baseline 25(OH)D.

19.4.2 Temporal patterns between biomarker measures and relapse

Blood will be taken at baseline, 1 week, 1 month, 2 months, 3 months, 6 months and 12 months after initiation of UVB phototherapy. Other than immunophenotyping of cells in freshly collected blood, all other preparations of blood, serum and peripheral blood mononuclear cells will be frozen and analysed at the end of the study. Differences in continuous responses between groups will be tested for significance using one-way ANOVA/t-tests or Kruskal-Wallis/Mann-Whitney tests as appropriate to the characteristics of the data. Covariate adjustment will be accommodated via general linear models. Comparisons of binary or categorical variables will be based on Fisher exact or Chi-squared tests, or logistical regression models to incorporate covariate adjustment. Repeated measurements over time will be analysed by longitudinal mixed models.

20. Data Management

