Intervention:	Participants will be randomised to either no phototherapy or narrow band UVB phototherapy, 3 times per week for 8 weeks. All participants will wear a UVB dosimeter.
No. Subjects:	60 CIS patients from Perth, Western Australia, and surrounding districts. There will be 2 groups of healthy individuals of similar age and sex recruited in Perth. The first group includes 10 healthy

	individuals donating blood monthly for 12 months for biomarker analysis. At recruitment, these individuals will have no known autoimmune disease and have not had a cold, flu or other illness in the last 7 days. They will not be taking strong immunomodulatory drugs. Measurement of biomarkers of these healthy controls from the same location as the CIS patients will allow precise comparison of the relative extent of change in biomarker expression by UVB phototherapy.
	Another group of up to 40 healthy individuals of similar age and sex in Perth will be invited to donate blood on a single occasion for analysis of their blood cells. These individuals will have no known autoimmune disease and have not had a cold, flu or other illness in the last 7 days. They will not be taking strong immunomodulatory drugs. Measurement and characterisation of blood cells from these healthy controls from the same location as the CIS patients will allow comparison of cell changes related to the clinical condition of the CIS patients when first diagnosed.
Study Duration:	Recruitment will occur all year round in Perth. Participants will participate for one year.
	punterpute for one year.
Objectives of the Study:	To test the hypothesis that narrow band UVB phototherapy compared with no phototherapy, is associated with a decreased risk of developing Multiple Sclerosis over 12 months following a first demyelinating event.

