- 6.3 Identification of MS biomarkers: transcriptional and immunophenotyping profiles. MS and its preclinical condition CIS are caused, at least in part, by pathogenic leukocytes that transit from lymphoid tissue to the brain via the peripheral circulation, with measurable changes in gene expression profiles in peripheral blood mononuclear cells associated with disease activity [39]. This paradigm is supported by studies on genetic susceptibility: most genes identified so far as associated with MS are primarily expressed in immune cells, especially involving the DC/T cell axis [10]. In the context of this proposal, recent advances by Investigator [name] and colleagues have identified specific transcriptional signatures associated with MS, which are also modified in a seasonally-dependent manner [40].
- 6.4 The intervention, Narrow band UVB phototherapy. Narrow band UVB phototherapy is a routine treatment for patients with psoriasis. As for psoriasis patients, a Wayne Electronics, Series M.S.1, phototherapy cabinet with output (between wavelengths 311-312 nm) of 0.6 mW/cm² will be used. Phototherapy will be given three times/week for eight weeks (24 exposures in total). Phototherapy will be delivered according to the Dundee protocol which is based on the patient's skin type. The starting dose of 20 mJ/cm² is based on knowledge of the skin type and will be well below the likely erythema threshold. Patients start with 40% increments on their initial dose, which will be reduced to 20% increments after 6 exposures. At each visit the dose given and any adverse effects will be recorded.

All participants will wear a calibrated UVB dosimeter (Scienterra Limited, Otago New Zealand). This will measure their UVB (as in sunlight) exposure. The UVB dosimeter is the size of a watch and is worn around the wrist. The dosimeter will collect daily UVB exposure data. The dosimeters will not be worn in the photobooth.

6.5 Known and potential risks and benefits of UVB phototherapy, if any, to human participants. Psoriasis has been successfully treated using narrow band UVB (TL-01) lamps with a 311 nm peak emission [1,2]. No increase in oncogenic risk for narrow band UVB phototherapy has

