been reported [2]. The face and eyes are protected during sessions of otherwise total body irradiation. Multiple mechanisms are involved in the control of psoriasis by narrow band UVB, including reduced inflammatory DCs infiltrating the skin [41], increased regulatory T cell number and function [8] and modulation of the IL-17/IL-23 axis [41].

A search of the literature has not revealed any studies of phototherapy for MS patients. There was one study of extracorporeal photochemotherapy used in 5 patients with refractory Relapsing Remitting MS with some success [42]. Phototherapy for MS patients is also supported by demonstration that UVR can suppress the severity of experimental autoimmune encephalomyelitis (a murine model of MS) when there were minimal changes in serum 25(OH)D levels [43].

This trial of narrow band UVB phototherapy will be documented in compliance with the protocol, GCP and the applicable regulatory requirements.

Description of the population to be studied. Patients at high risk of MS [patients with CIS defined by a First Demyelinating Event (FDE)].

7. Hypothesis, Aims and Objectives

Hypothesis: Narrow band UVB phototherapy will benefit patients with CIS; it will alter in a sustainable manner the immunological biomarkers in blood that are associated with subsequent transition to clinically-definite MS. UVB phototherapy will increase the ratio of regulatory to effector T lymphocytes, reduce the functional capacity of circulating dendritic cells (DCs), and ensure that the transcriptional profile in their peripheral blood mononuclear cells is similar to one associated with healthy controls and not one characterised for MS patients.

Aims and Objectives of the PhoCIS trial: In 30 patients with CIS given a course of narrow band UVB phototherapy (3 exposures/week for 8 weeks) and 30 CIS patients without phototherapy wearing UVB dosimeters, we will examine whether:

- 1. UVB phototherapy reduces the risk of a recurrent disease activity (clinical demyelinating event or MRI activity) in the 12 months following onset of a first demyelinating event.
- 2. UVB phototherapy affects the clinical and/or radiological responses associated with development of MS in high-risk CIS participants.
- 3. UVB phototherapy alters the phenotype, function and transcriptional profile of immune cells in blood drawn 1 week, and 1, 2, 3, 6 and 12 months after initiation of phototherapy in comparison with those in blood taken immediately before phototherapy.

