10.3.1 Sun exposure

Participants will be asked to avoid tanning salons and sun beds. Reference material on the current sun exposure guidelines, as advised by the Cancer Council Australia, will be provided on request (www.cancerwa.asn.au/prevention/sunsmart). Participants should not stay in the sun for sufficient time to cause reddening of the skin. This trial is being performed in winter to avoid sun exposure.

A silicone skin cast of the back of the hand will be prepared from all participants. This will allow us to test whether past sun exposure modifies the immune response to phototherapy. This provides a reliable and validated estimate of actinic damage secondary to cumulative sun exposure [17,44].

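### The protocol says both that the trial runs in winter and that it recruits all year, while its season-dependent transcriptome endpoint is sized on winter data and no model names season

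*Protocol*

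**What the plan says.** **When the trial runs.** Section 10.3.1 states "This trial is being performed in winter to avoid sun exposure". The Synopsis (Study Duration) states "Recruitment will occur all year round in Perth". Section 9 invites all CIS patients presenting in 2014, 2015 and 2016. Section 19.3 (repeated in 8.7 and the Synopsis) foresees study of seasonal effects, and section 8.1 bleeds ten healthy controls monthly partly to compare seasons.

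**Why season bears on the endpoint.** Section 8.6 lists whole-blood transcriptome change first among the primary endpoints. Section 6.3 says of the MS transcriptional signatures that they are ones "which are also modified in a seasonally-dependent manner". The transcriptome sample size in section 19.3 is "based on standard deviation and means for each gene in winter", giving 11 to 27 patients.

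**Comparison and models.** Aim 3 (Synopsis and section 7) assesses immune cells after the start of phototherapy "in comparison with those in blood taken immediately before phototherapy". Section 19.4.2 compares arms: "Differences in continuous responses between groups will be tested for significance using one-way ANOVA/t-tests or Kruskal-Wallis/Mann-Whitney tests". It continues "Covariate adjustment will be accommodated via general linear models" and assigns repeated measurements to longitudinal mixed models, without naming covariates. Section 8.4 randomises "with matching on demographic variables (age and sex) to optimize balance between groups". Section 19.4.1 names covariates for the time-to-event models, among them age, sex, recent sun exposure and baseline 25(OH)D, but not calendar season.

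**The concern.** The intervention is ultraviolet light, the leading endpoint is described as seasonal, and the protocol gives two incompatible accounts of when patients are treated. A reader cannot tell which population of samples the 11 to 27 figure describes, or whether season is meant to be held constant by design or handled in the analysis.

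The wording of aim 3 adds to this. A before-after change within treated patients carries the calendar shift between samples, recovery from the first event, and the vitamin D prescribed to all patients (sections 8.1 and 10.1). The randomised comparison separates UVB from all three. If results were reported against aim 3 as worded, the benefit of the control arm would be lost for that aim.

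**Working it through.** **1. Can the season statements be reconciled?** Suppose recruitment is all year but phototherapy is given only in winter, taken as June to August in Perth (assumption). Section 13 requires that a patient can receive the first session within 120 days of symptom onset. Counting 120 days from 1 February reaches 1 June (27 + 31 + 30 + 31 + 1 = 120). Patients with onset from September to January would therefore reach day 120 before winter, with the previous winter already over. That cannot sit beside inviting all patients who present. The two statements conflict.

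**2. Does the winter basis fit under either reading?** Section 8.2 samples at baseline, 1 week, and 1, 2, 3, 6 and 12 months.
- All-year recruitment: baselines and follow-ups fall in every season.
- Winter recruitment: a June start gives samples in July, August, September, December and the next June. The 6-month sample is in summer.

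Winter means and SDs describe only part of the samples in either case.

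**3. Can 11 to 27 be reproduced?** No. The mean differences, SDs, power and sidedness are not given, nor is it stated whether the figure is per arm or paired. Back-solving at an assumed 80% power and two-sided 5%, with 1.960 + 0.842 = 2.802:
- per arm, d = 2.802 × √(2/n): 1.19 SD at n = 11 and 0.76 SD at n = 27;
- paired within patient, d = 2.802/√n: 0.84 SD and 0.54 SD.

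For reference, 30 per arm gives 2.802 × √(2/30) = 0.72 SD. These values are in winter SD units. The documents do not allow conversion to year-round units.

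**4. What does aim 3 mix in?** Under the winter reading, every baseline is a winter sample and every 6-month sample a summer one, so the before-after change at 6 months is fully confounded with season. Under the all-year reading, seasonal shifts tend to average out across patients but add variance. Recovery and vitamin D remain mixed in under both. Section 8.2 bleeds both arms on the same visit schedule, so the between-arm difference in change removes these on average.

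**5. What does leaving season out of the model cost?** Assume season explains a share R² of the outcome variance (not in the documents), 30 per arm, a true effect of 0.5 SD and two-sided 5%. Power = Φ(0.5/√(2(1 − R²)/30) − 1.96).

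| R² | power with adjustment |
|---|---|
| 0 (no adjustment) | 49% |
| 0.1 | 53% |
| 0.2 | 58% |
| 0.3 | 64% |

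Type I error is not inflated. If allocation were perfectly balanced on covariates with that R², as matching on age and sex aims for those two factors, an unadjusted test would have actual alpha 2(1 − Φ(1.96/√(1 − R²))) = 0.039, 0.028 and 0.019. It would be conservative.

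**The case against.** A reader who stops at the sentence on t-tests and rank tests might infer that continuous outcomes are analysed only by unadjusted tests that ignore baseline. The document does not support this. The next sentence provides general linear models for covariate adjustment, the paragraph ends with mixed models for repeated measurements, and the clinical and MRI secondary endpoints are changes from baseline. Which covariates enter and which analysis leads may be settled in a statistical analysis plan that is not shown, so their absence is no error here.

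Two larger numbers are also tempting.
- Comparing ANCOVA with an unadjusted change score gives a variance ratio of (1 + r)/2: 0.75 at r = 0.5 and 0.65 at r = 0.3, so 60 patients would act like 80 to 92. This is not a gain over a plan that already provides adjusted models. With r = 0.8 or 0.9 the equivalent is only 67 or 63, and the documents give no r.
- Dividing by one minus a seasonal share of 10% to 30% would inflate 11 to 27 by 1.1 to 1.4. This assumes both the share and that the winter SD equals a season-free residual SD that carries over to change.

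It is also fair that season is not ignored: there are monthly healthy controls, UVB dosimeters, and adjustment for recent sun exposure in the time-to-event models. The stem of the aims in section 7 covers both arms, and chance seasonal imbalance under randomisation is random error, not systematic bias.

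These points narrow the concern. They do not remove the contradiction on when the trial runs, the winter-only basis of the sample size, or the comparator in aim 3. All three are statements of the protocol itself.

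**Conclusion.** The contradiction between section 10.3.1 and the Synopsis, section 9 and section 19.3 stands and must be resolved in the protocol. It is consequential because it touches a primary endpoint that the protocol itself calls seasonal, and because the 11 to 27 figure describes winter samples only, under either reading of recruitment. Aim 3 names a before-after comparator where the analysis section uses the randomised groups; this is a fault of wording, since the data for the right contrast are collected.

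Naming season and the matching factors in the models is a recommendation, not the correction of an error. Its value depends on a seasonal variance share and baseline correlations that the documents do not give. On the assumed range of 10% to 30% for season, it is worth about 4 to 15 percentage points of power at 0.5 SD (53 − 49 and 64 − 49). Leaving these covariates out does not raise the false-positive rate of the between-arm test.

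**What to change.** 1. Reconcile section 10.3.1 with the Synopsis, section 9 and section 19.3, so that one statement of when patients are recruited and treated holds throughout. The investigators must say which is intended.
2. In section 19.3, and where it is repeated in section 8.7 and the Synopsis, label 11 to 27 as winter-based or restate it with year-round SDs, giving the effect size, SD, power, sidedness and whether the number is per arm.
3. Reword aim 3 in the Synopsis and section 7 as the between-arm difference in change from baseline.
4. In the general linear and mixed models of section 19.4.2, name baseline value, age, sex and sampling date as covariates, with date entered as an annual sine and cosine pair.

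Items 1 to 3 are wording, apart from any restated calculation. Item 4 uses data already collected and costs 1 + 1 + 1 + 2 = 5 degrees of freedom.
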